11.5 Analysis Methods

11.5.1 Timing of Analysis

A single and final analysis will occur after 66 enrolled subjects have been identified in the evaluable population.

11.5.2 Subject Disposition

A summary of all consented subjects will be provided. This will include a summary of subjects who consented, were enrolled, treated, discontinued treatment (including reasons), died, were lost to follow-up or withdrew consent.

11.5.3 Baseline Subject Characteristics

A summary of subject demographics will be completed and selected subject medical history will be assessed.

11.5.4 Primary Analysis

The frequency and proportion of subjects who experienced at least a 2-point improvement in neuropathy between the baseline score and the score obtained at Week 10 (+/- 1 week) will be calculated for each study arm. A two-sided Fisher Exact test will be executed, testing the null hypothesis that there is no difference in neuropathy improvement rate between the arms.

Additionally, logistic regression will be used to evaluate the impact of acupuncture while adjusting for potential baseline confounding factors, including the stratification variable, baseline neuropathy severity grade. Univariate models will be used to identify baseline factors that are individually prognostic. Statistically significant factors identified from the univariate models will then be included in a multivariable model. Backward elimination will be used to identify baseline factors that are independently prognostic. A treatment indicator variable will be added to obtain an adjusted odds ratio.

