4. SUBJECT ALLOCATION

4.1 Randomization

Subjects will be randomized in a 2:1 fashion to either acupuncture plus standard subject management or standard of care alone and assigned a Sequence Number. This will be accomplished utilizing the CTMS, whereby a list of Sequence Numbers and associated treatment arm assignments randomly generated prior to study activation will be uploaded by a member of the Levine Cancer Institute Biostatistics Core. The Sequence Number will be a four digit, randomly generated ID number, ranging from 0001 to 9999. A stratified block randomization will be utilized including the following stratification factors to reduce confounding of comparisons between the treatment arms:

- Baseline neuropathy score (neuropathy score 2 – 6 vs 7 – 10)

Blinding will not be possible within this trial because the subjects and study personnel will be able to decipher intervention from control based on the study activities. Those exposed to acupuncture will understand that they are in the intervention group and those given standard of care only will understand that they are in the control group. If a subject in the control group has an acupuncture session while enrolled, they will be discontinued from the study and all further assessments at that point.

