11.2 Sample Size

This study is designed with a primary objective to evaluate the effectiveness of acupuncture versus standard subject management in terms of reduction of neuropathy in actively treated multiple myeloma subjects diagnosed with CIPN. A Fisher's Exact Test with a two-sided alpha = 0.20 significance level will have at least 80% power to detect the difference between a standard of care group proportion of 0.10 and a treatment group proportion of 0.35 when the sample sizes are at least 22 and 44 evaluable subjects, respectively. In order to identify at least 66 evaluable subjects, we anticipate enrolling 75 subjects.

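### Fisher's exact test is valid and meets its stated power, but Boschloo's exact test would gain about 3.5 points of power at 22/44 and 0.10 v 0.35 within the same 0.20 error limit

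*Combined protocol and SAP*

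**What the plan says.** The primary endpoint (11.3.1) is binary: an improvement of two or more points on the 0-10 neuropathy scale from baseline to Week 10. For its comparison, 11.5.4 says: "A two-sided Fisher Exact test will be executed, testing the null hypothesis that there is no difference in neuropathy improvement rate between the arms".

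Section 11.2 bases the sample size on the same test: "A Fisher's Exact Test with a two-sided alpha = 0.20 significance level will have at least 80% power". The rates are "a standard of care group proportion of 0.10 and a treatment group proportion of 0.35", and the power holds "when the sample sizes are at least 22 and 44 evaluable subjects, respectively". The statistical paragraph of the synopsis gives the same design. Section 4.1 allocates 2:1 in favour of acupuncture.

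Section 11.5.1 provides for one analysis, triggered when 66 evaluable subjects have been reached in total. It sets no minimum per arm. Section 11.5.5 repeats a similar analysis at Week 5.

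The documents do not give the actual error rate of the test, do not say how the two-sided p-value is formed, and do not discuss another exact test.

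**The concern.** Fisher's test conditions on the total number of responders. With 66 subjects this leaves few possible p-values for each total, so the test usually cannot come close to its nominal level. The sponsor has accepted a lenient 0.20 in order to get adequate power from a small trial. If part of that allowance goes unused, real effects are missed more often than the design's own error limit requires. There is a single analysis, so no interim look accounts for the unused part.

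An unconditional exact test gives the same guarantee of at most 0.20 with less waste. At stake is a few points of power on the primary comparison. Validity is not in question.

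**Working it through.** **Inputs.** Two-sided 0.20; rates 0.10 and 0.35; 22 control and 44 acupuncture subjects (all from 11.2). The pooled design rate is (22 × 0.10 + 44 × 0.35) / 66 = 17.6 / 66 = 0.267.

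**Method.** List all 23 × 45 outcomes (x of 22, y of 44).
- Fisher p(x, y) is the sum of hypergeometric probabilities, given x + y, that are no larger than that of the observed table. Reject if p ≤ 0.20.
- Power is the sum over rejecting tables of Bin(x; 22, 0.10) × Bin(y; 44, 0.35).
- Actual error at common rate π is the same sum with π in both arms.
- Boschloo p is the maximum over π of the probability, under π in both arms, of a Fisher p no larger than the one observed. Reject if it is ≤ 0.20.

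**1. The plan's own figure.** Fisher power is 81.7%, so at least 80% is confirmed.

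**2. Actual error of the planned test at 22/44.**

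| Common rate | 0.10 | 0.15 | 0.20 | 0.25 | 0.267 | 0.30 | 0.35 | 0.40 | 0.50 |
|---|---|---|---|---|---|---|---|---|---|
| Error | 0.125 | 0.143 | 0.149 | 0.149 | 0.151 | 0.158 | 0.172 | 0.183 | 0.192 |

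The error lies between 0.125 and 0.155 for common rates from about 0.10 to 0.29. The unused share is (0.20 − 0.125) / 0.20 = 37% at 0.10 and (0.20 − 0.151) / 0.20 = about 25% at 0.267. At 0.50 it is only (0.20 − 0.192) / 0.20 = 4%.

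**3. Boschloo's test at 22/44.** It rejects when Fisher's p is at most 0.252, and its maximum error is 0.198. It rejects every table that Fisher rejects and 14 more. This nesting holds by construction: Fisher's test at level p has error at most p for every π, so Boschloo's p cannot exceed Fisher's. Power at 0.10 v 0.35 is 85.1% (85.15 − 81.67 = about 3.5 points). The risk of missing the design effect falls from 18.3% to 14.9%. For scale, Fisher's test reaches 85.1% at 23/47, which is 70 evaluable subjects.

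An example is 3/22 v 13/44 responders. Fisher's p is 0.226 and Boschloo's is 0.192.

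**4. Dependence on the split** (0.10 v 0.35, total 66).

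| Split | Fisher | Boschloo | Gain (points) |
|---|---|---|---|
| 20/46 | 79.3% | 83.5% | 4.2 |
| 21/45 | 81.0% | 85.0% | 4.0 |
| 22/44 | 81.7% | 85.1% | 3.5 |
| 23/43 | 83.7% | 85.6% | 1.9 |
| 24/42 | 82.9% | 82.9% | 0.0 |

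If all 75 enrolled were evaluable (25/50), the gain would be 0.4.

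**5. Dependence on the rates** (22/44).

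| Rates | Fisher | Boschloo | Gain (points) |
|---|---|---|---|
| 0.10 v 0.30 | 67.6% | 71.9% | 4.3 |
| 0.15 v 0.35 | 63.1% | 68.0% | 4.9 |
| 0.20 v 0.45 | 76.2% | 77.4% | 1.2 |
| 0.25 v 0.50 | 75.1% | 75.4% | 0.2 |
| 0.30 v 0.55 | 74.4% | 74.4% | 0.0 |

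The last three rows keep the plan's 25-point difference.

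**6. Definition of two-sided.** If the p-value is formed by doubling the smaller tail, Fisher's power at 22/44 is 78.5% and its maximum error is 0.139. Boschloo's test built from doubled one-sided p-values has 85.2% power.

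**The case against.** The strongest reply is that nothing is wrong. The trial is sized on Fisher's test and analysed with Fisher's test, its power claim is met, and its error stays below 0.20. Choosing between two valid exact tests can be called a matter of taste. This stands in full as a defence of the plan's validity. It does not answer the point that the alternative never rejects less often and keeps the same limit.

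Second, the gain is local. The documents give no source for the control rate of 0.10, and 11.5.1 fixes only the total. At 24/42, or with the same difference from a control rate of 0.30, nothing is gained. This also stands, and the size of the gain must be stated with its conditions.

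Third, the extra rejections are marginal. Seven of the 14 tables favour control, and only three favour acupuncture with a control rate below 0.60: 1/22 v 7/44, 3/22 v 13/44 and 4/22 v 15/44. In all 14, Fisher's p lies between 0.201 and 0.252, so the report could show a significant Boschloo result beside a Fisher p-value above 0.20. This is a real presentational cost.

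A reader might go further in three ways that the documents do not support:
- That the trial is underpowered or its test invalid. The 81.7% and the maximum error of 0.192 contradict this.
- That a quarter or more of the error allowance is always wasted. That holds only for low common rates.
- That the power claim fails because the doubled-tail version gives 78.5%, or because a 20/46 split gives 79.3%. The documents do not specify doubling, the usual definition reproduces their claim, and 11.2 makes the claim only for at least 22 and 44.

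**Conclusion.** This is a cheap improvement to a valid plan and does not correct an error. At 22/44 and 0.10 v 0.35, Boschloo's test at a two-sided 0.20 has 85.1% power against 81.7%, with maximum errors of 0.198 and 0.192. The gain of about 3.5 points assumes exactly that split and those rates, and that Fisher's two-sided p-value sums the tables no more probable than the one observed. Across nearby splits of 66 it ranges from 0 to 4.2 points. With a 25-point difference it falls to about 1 point or less once the control rate is 0.20 or higher. It is never negative, because with this definition Boschloo's test rejects wherever Fisher's does.

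**What to change.** Amend the protocol before any outcome data are analysed by arm. The timing matters because the trial is open-label and the new test rejects more often.

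- **11.5.4:** name Boschloo's unconditional exact test at two-sided 0.20 as the primary test. State that the statistic is the two-sided Fisher p-value (the sum of probabilities of tables no more probable than the observed one), maximised over the common improvement rate. Report Fisher's p-value as a secondary display.
- **11.5.5:** use the same test for the Week 5 repeat.
- **11.2 and the synopsis:** name the same test and give the power as about 85% if the evaluable split is 22/44 and the rates are 0.10 v 0.35.
- **Programming:** check that the software uses the stated two-sided definition, since a version that doubles the one-sided p-value is a different test.

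No subjects, visits or data are added. The costs are an amendment, which under 13.3.1 needs approval by the Sponsor-Investigator and the Sponsor IRB, a test that readers know less well, and the possibility of a Boschloo result significant at 0.20 beside a Fisher p-value of up to 0.252.

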5.3.2 Medical History

The medical history information to be collected at baseline only, includes:

- Peripheral (sensory) neuropathy Grade by CTCAE 5.0 criteria⁶⁸ (only if recorded in medical record)
- MM diagnosis date and staging
- ECOG performance status⁶⁹
- Body mass index (BMI) calculated by height and weight
- History of diabetes (excluding gestational diabetes)
- Cardiovascular disease
- Chronic kidney disease
- Vertebral fractures

- Current chemotherapy regimen and all bortezomib/bortezomib-combination treatment given prior to enrollment

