11.5.5 Secondary Analysis

An analysis similar to that described in the primary analysis will be performed for scores obtained at 5 weeks. Additionally, a repeated measures model including a random effect for subject will be estimated for the binary neuropathy improvement score measured at baseline,

week 5 and week 10. Additional baseline factors as previously described above may be added to this model as well.

The secondary endpoint composite measure of specific CIPN symptoms will be treated as a continuous measure and analyzed using analysis of variance techniques. The secondary endpoints measured on a 5-level ordinal scale will be summarized with frequencies and proportions and analysis of variance techniques on the ranks test will be used to test for differences by arm. The number of unhealthy days and activity limitation days will be analyzed using analysis of variance techniques.

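### The supportive adjusted odds ratio rests on data-driven covariate selection with no threshold or candidate list and about 17.6 improvers expected; a fixed arm-plus-stratum model would be better.

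*Combined protocol and SAP*

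**What the plan says.** Section 11.5.4 makes the two-sided Fisher exact test the primary test. It then adds a logistic regression that adjusts the acupuncture effect for possible baseline confounders, "including the stratification variable, baseline neuropathy severity grade". Factors are screened one at a time, and "Statistically significant factors identified from the univariate models will then be included in a multivariable model". Then "Backward elimination will be used to identify baseline factors that are independently prognostic", and finally "A treatment indicator variable will be added to obtain an adjusted odds ratio".

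The plan does not state:
- a significance level for screening or elimination (the 0.20 level is given only for the Fisher test, in section 11.2 and the synopsis);
- any candidate covariate besides the stratification variable (sections 5.3.1 and 5.3.2 list 8 + 9 = 17 baseline items to collect, but nothing designates them as candidates);
- a rule that keeps the stratification variable if it is not significant.

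Section 4.1 lists one stratification factor, the baseline 0–10 score split at 2–6 and 7–10. Section 11.5.5 extends the approach: "An analysis similar to that described in the primary analysis will be performed for scores obtained at 5 weeks". Of the repeated measures model it says: "Additional baseline factors as previously described above may be added to this model as well".

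**The concern.** This is the only adjusted effect estimate that section 11.5.4 plans, and it sits beside the primary result. As written, two competent analysts could follow the section and report different odds ratios from the same data, because each must supply the threshold and the candidates. The trial is open-label (section 4.1), and nothing in the plan separates those choices from knowledge of results by arm.

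With few improvers, significance screening tends to miss real predictors and to admit chance ones. The randomization factor may itself fail the screen, although the opening sentence of the paragraph shows an intent to adjust for it. Because section 11.5.5 asks only for a similar Week 5 analysis and makes covariates optional in the repeated measures model, the adjustment set could also differ across three analyses of one outcome.

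**Working it through.** **Inputs from the plan (sections 11.2 and 4.1).** Improvement rates 0.10 (control) and 0.35 (acupuncture); 22 and 44 evaluable subjects; Fisher exact test, two-sided alpha 0.20; 2:1 allocation; one binary stratum.

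**Plan's own figure.** Enumerating all 23 × 45 possible tables with the two-sided Fisher p-value gives power 0.817, which agrees with the stated power of at least 80%. Nothing below touches this test.

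**Information available to the logistic model.** Expected improvers = 22 × 0.10 + 44 × 0.35 = 2.2 + 15.4 = 17.6. Per model term this is 17.6/2 = 8.8 for arm plus stratum, 17.6/5 = 3.5 for five terms and 17.6/10 = 1.8 for ten.

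**Does the stratum survive the screen?** The documents give neither the share of subjects scoring 7–10 nor the stratum's prognostic strength, so both are assumed. With a share of 20–50% and an odds ratio of 1.5–3 (200,000 simulated trials per setting, likelihood-ratio test of the stratum alone), it fails the screen in 56–92% of trials at 0.05, 43–85% at 0.10 and 28–71% at 0.20.

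**How often does noise enter?** With 9 independent noise factors, the nominal chance that at least one passes the screen is 1 − 0.95^9 = 0.37 at 0.05 and 1 − 0.80^9 = 0.87 at 0.20. After the full procedure, the simulation below kept at least one in 24–31% and 76–84% of trials.

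**Full procedure, simulated.** Assumed inputs:
- 66 subjects, 36% in the high stratum (24 high, 42 low), arms 2:1 within each stratum;
- marginal rates held at 0.10 and 0.35, stratum odds ratio 2–6;
- 10 candidates: the stratum, 4 binary and 5 continuous noise factors;
- univariate Wald screen, backward elimination at the same level, treatment added last;
- 5,000 trials per setting (Monte Carlo standard error at most 0.7 points), leaving out the roughly 9% of trials with no control improver from the odds ratio and power comparisons.

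Two odds ratios are counted as different when |OR1/OR2 − 1| > 0.20.

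| Comparison | Share of trials differing by more than 20% |
|---|---|
| p<0.05 v p<0.20, stratum screened | 21–25% |
| Same, 5 candidates | 9–12% |
| p<0.05 v p<0.20, stratum forced in | 21–25% |
| Stratum forced v screened, same threshold | 0.4–2% |
| Selection at p<0.05 v fixed arm + stratum | 11% |
| Selection at p<0.20 v fixed arm + stratum | 28–31% |

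At a stratum odds ratio of 3, the stratum stays in the final model in 40% of trials at p<0.05 and 66% at p<0.20. Repeat simulations at that odds ratio gave 23% and 25% for the first row. The second and third rows show where the movement comes from: the number of screened noise factors drives it, and forcing the stratum in leaves it unchanged.

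**Error rate.** With both arms at 0.267 and a stratum odds ratio of 3, rejection at 0.20 was 0.20–0.21 under selection and 0.20 under the fixed model.

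**Scale of a 20% shift.** The planning odds ratio is (0.35/0.65)/(0.10/0.90) = 4.85. The standard error of its log is √(1/2.2 + 1/19.8 + 1/15.4 + 1/28.6) = 0.78. A 20% shift is ln 1.2 = 0.18 or |ln 0.8| = 0.22, so 0.23 to 0.29 of one standard error. The 95% interval extends by a factor of exp(1.96 × 0.78) ≈ 4.6 each way.

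**The case against.** The strongest reply is that no inferential harm is shown. The logistic model is supportive and carries no alpha or decision rule, and the shifts measured above are small beside the interval that would be reported. That stands, and it limits the weight of the point.

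The simulation also makes every candidate except the stratum pure noise, which rules out any benefit from selection. With one or two truly prognostic factors added (assumed odds ratio 4), the power advantage of the fixed model at two-sided 0.20 was 0.4–0.6 points in four of six settings, 1.9 in one and −0.3 in one. With noise only it was 1.0–1.4 points against p<0.05 selection and 2.1–3.1 against p<0.20. The odds ratios differed more often (32–62%), but part of that is adjustment for real predictors and non-collapsibility. So the gain from fixing the model would be smaller if good predictors are among the candidates.

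Three stronger readings might be inferred, and the documents do not support them:
- **That losing the stratum is the main damage.** Naming it as an adjustment factor can fairly be read as always keeping it. Even if it is screened, forced and screened versions seldom differ materially (0.4–2% of trials).
- **That the model would use the wrong neuropathy variable.** Section 5.3.2 separately collects "Peripheral (sensory) neuropathy Grade by CTCAE 5.0 criteria", and only where it is on record. But in section 11.5.4 the words severity grade stand in apposition to the stratification variable, and section 4.1 has only one. This is loose wording.
- **That sparse control data are part of this problem.** The chance of no control improver at the planning rate is 0.9^22 = 9.8%. It would affect a fixed model equally, so it is a separate matter and not part of this point.

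**Conclusion.** The point holds as one about a supportive analysis. Section 11.5.4 prescribes a data-driven selection procedure where a simple fixed model is available from data already collected. It leaves the threshold and candidates open, and its steps do not ensure that the randomization factor stays. Under the assumed inputs, the unstated threshold alone moves the adjusted odds ratio by more than 20% in about 21–25% of trials with 10 candidates and 9–12% with 5, mostly through screened noise factors. These figures measure dependence on the analyst's choices. They are not error rates, and they would change with the real number and strength of the candidates.

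A reader might infer that the trial's conclusion or its error control is at risk. It is not: the Fisher test does not use this model, and simulated type I error under selection stayed at 0.20–0.21. The change is still worth making before analysis, because it removes an avoidable choice at little cost.

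**What to change.** 1. Keep the Fisher test as primary.
2. In section 11.5.4, replace the screening and elimination steps with one pre-specified logistic model containing arm and the randomization stratum (baseline score 2–6 v 7–10), kept regardless of significance. Name any further covariates in advance and keep them few.
3. In section 11.5.5, use the same covariates for the Week 5 analysis and the repeated measures model, and state this as a requirement.
4. Report any search for prognostic factors separately, labelled exploratory.
5. As an editorial tidy-up, use the section 4.1 term for the stratum in section 11.5.4.

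The cost is analysis-plan wording only, with no new data and no change in sample size. The downside is that the main adjusted model no longer looks for unplanned prognostic factors; item 4 keeps that search available.

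### For the Week 10 primary endpoint the only named between-arm effect measure is an adjusted odds ratio with no interval and no rule for an empty control cell, which at the design rates makes a standard fit infinite in about 10% of trials.

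*Combined protocol and SAP*

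**What the plan says.** Section 11.5.4 (Primary Analysis) has two steps. First, the number and proportion of subjects improving by at least 2 points are tabulated by arm and compared with a two-sided Fisher test. Second, as an addition, a logistic model is built from baseline factors, and then: "A treatment indicator variable will be added to obtain an adjusted odds ratio". No estimation method is named for that model. No confidence interval, risk difference, risk ratio or unadjusted odds ratio is specified.

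Section 11.2 gives the design rates, "a standard of care group proportion of 0.10 and a treatment group proportion of 0.35", with the sample sizes: "when the sample sizes are at least 22 and 44 evaluable subjects, respectively".

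Section 11.5.5 carries the approach to the midpoint: "An analysis similar to that described in the primary analysis will be performed for scores obtained at 5 weeks". It also plans a random-effect repeated measures model for the binary outcome and analysis of variance for the secondary endpoints, without naming an effect measure for either. The only intervals specified in section 11 are the Clopper-Pearson intervals for adverse events of special interest in the acupuncture arm (11.5.6).

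**The concern.** The design expects 22 × 0.10 = 2.2 improvers in the control arm. With so few, an empty control cell is a realistic result. If no control improves and at least one acupuncture subject does, the maximum-likelihood treatment coefficient has no finite value. Adding covariates cannot prevent this: lowering the intercept and raising the treatment coefficient by the same amount leaves every acupuncture subject's fitted probability unchanged and always improves the fit to the controls.

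At stake is the reported size of effect. The test runs at a two-sided 0.20 level, so the p-value alone is modest evidence and readers will rely on the estimate and its precision. If the named estimate does not exist, the analyst must choose a substitute after seeing the results of an unblinded trial. A prespecified method avoids that.

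**Working it through.** **Inputs.** From 11.2: 22 control and 44 acupuncture evaluable subjects, improvement rates 0.10 and 0.35, two-sided Fisher test at 0.20, and 75 enrolled to reach 66 evaluable. From 4.1: 2:1 allocation.

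**The plan's own figure.** Summing the two binomial distributions over all 23 × 45 possible tables, and counting those with a two-sided Fisher p-value of 0.20 or less, gives power of 81.7%. The plan's statement of at least 80% is reproduced.

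**True odds ratio at the design rates.** (0.35/0.65) / (0.10/0.90) = 4.85. This is the unadjusted value. The adjusted value depends on covariate effects that the documents do not give.

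**Chance of an empty control cell.** P(none of n controls improves) = (1 − rate)^n.

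| Controls | Control rate | P(no control improver) |
|---|---|---|
| 22 | 0.10 (design) | 9.8% |
| 25 (all 75 evaluable) | 0.10 | 7.2% |
| 22 | 0.05 | 32% |
| 22 | 0.15 | 2.8% |
| 22 | 0.20 | 0.7% |

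Nearly all the empty-cell trials at the design rates are significant. The share among significant trials is therefore 9.85/81.7 = 12.1%.

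**Distribution of the unadjusted maximum-likelihood odds ratio** (same enumeration, 22/44, 0.10 against 0.35):

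- median 5.17, 75th percentile 10.0, 90th percentile 23.0
- at least twice 4.85: 28.1% (9.8% infinite, 18.2% finite)
- at least three times 4.85: 15.9% (9.8% infinite, 6.1% finite)
- half of 4.85 or less: 15.2%

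One control improver (probability 24.1%) with 15/44 in the acupuncture arm gives (15 × 21)/(29 × 1) = 10.9. Two control improvers give (15 × 20)/(29 × 2) = 5.17. A single control subject moves the estimate by a factor of two.

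**With covariates.** In simulations of 6,000 trials per scenario with one or three binary baseline factors, maximum likelihood was infinite in 7 to 10% of trials and at least double the true conditional value in 28 to 30%. The prevalence (40%) and effects (log odds ratio 0 or 0.7) are assumptions. The enumerated figures above need none.

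**The proposed alternatives.** In a treatment-only model, Firth's method is equivalent to adding 0.5 to each cell. Enumerated the same way, that estimate is always finite, with median 4.31 and 90th percentile 13.7, and it is at least double the truth in 16%. The difference in proportions is also always finite: mean 0.25, 10th to 90th percentile 0.14 to 0.36.

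**Example.** Take 0/22 against 15/44, for which Fisher p = 0.001.

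- The maximum-likelihood odds ratio is infinite.
- The Firth-type value is (15.5 × 22.5)/(29.5 × 0.5) = 23.6, finite but plainly imprecise.
- The risk difference is 15/44 = 0.34, with Newcombe intervals of 0.23 to 0.44 (80%) and 0.15 to 0.49 (95%).

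**The case against.** The strongest reply is that the primary inference is sound. The trial is sized on Fisher's test, which an empty cell does not disturb, and the logistic model is supplementary. This stands: the point concerns estimation, not the test.

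A reader might infer that the odds ratio is the only between-arm estimate in the whole plan. The documents do not support that. Arm proportions are planned, so a difference can be obtained by subtraction, and 11.5.5 adds other between-arm models. What is missing is a named difference, an interval for it, and any provision for an empty cell.

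A reader might also infer that the odds ratio is badly biased upward. The enumeration does not show that: the median is close to the truth and 15% of estimates are at half the truth or less. Much of the spread is the two-sided imprecision that comes with 22 controls.

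Nor is an empty control cell always a favourable result. With 0/22 against 4/44, Fisher p = 0.29. Nor is the trial left with no information: for 0/22 against 15/44, the ordinary likelihood still gives a 95% profile lower limit of about 5.2 for the odds ratio, with no upper limit.

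Finally, the plan says only that logistic regression will be used, so maximum likelihood is an inference from the usual meaning of the term, and the plan names no Wald interval. The 9.8% also depends on the control rate and falls quickly above 0.10. Both reservations are fair. Neither supplies the missing interval or the missing rule.

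**Conclusion.** The point holds as an inexpensive improvement to the reporting of the primary endpoint. At the design assumptions of 22 controls and a 0.10 control rate, a standard maximum-likelihood fit of the one named effect measure is infinite in 9.8% of trials and in 12.1% of those significant at 0.20. In 28% of trials the unadjusted estimate is at least twice the true 4.85, counting the infinite ones. The first figure ranges from 2.8% at a control rate of 0.15 to 32% at 0.05, and is 7.2% if 25 controls are evaluable at 0.10. The Week 5 repeat has the same gap. The plan gives no Week 5 rate, so its size there is unknown.

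These figures rest on the plan's own rates and on reading logistic regression as maximum likelihood. They do not call the Fisher test, its power or the arm proportions into question.

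**What to change.** In 11.5.4, and by reference in the Week 5 repeat in 11.5.5:

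1. State that the adjusted treatment odds ratio will be estimated by Firth penalised-likelihood logistic regression and reported with a profile-likelihood confidence interval.
2. State that the difference in improvement proportions will be reported beside the Fisher p-value with a Newcombe or exact unconditional confidence interval. Name one method and the confidence level in advance. An 80% interval corresponds to the test's 0.20 level, and a 95% interval can be given as well.

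The cost is SAP wording and a little extra analysis work. No new data, subjects or procedures are needed, and the primary test is unchanged. Firth's method shrinks the odds ratio slightly (enumerated median 4.31 against 5.17, with a true value of 4.85). It guarantees a finite estimate but does not remove the imprecision. Exact logistic regression, or a written fallback for an empty cell, would also close the gap in the odds ratio if the sponsor prefers it.
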